## **15 PLANNED ANALYSIS**

### **15.1 Final**

Data cleaning and preparation process will be carried out prior to analysis.

All patients enrolled will be followed up and included unless they withdrew from the study before the administration of the first dose. An intention to treat analysis will be carried out. Per protocol analyses may also be carried out alongside the intention to treat analysis if necessary. The analyses will mostly consist of tables of data such as mean values (or geometric means if the data is log normal) together with standard deviations and ranges. For data such as scores, medians, and ranges may be used instead, and binary outcome variables will use percentages. Comparisons against baseline will be made using Student's t-tests for paired and unpaired samples; Mann-Whitney U test; Wilcoxon matched pairs test; p values <0.05 will be considered significant.

Since the primary aim of the study is to provide patient safety data and guide the development of an antigen specific immunotherapy programme, it may be a requirement for strategic planning of subsequent stages of clinical study development, that early analysis of trial data is conducted.

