### **4.4 Secondary endpoints**

- T cell responses to C19-A3 GNP as determined by changes from baseline of interferon gamma and IL-10 ELISPOT responses to this peptide in blood following treatment at weeks 0, 9 and 14.
- T cell responses to C19-A3 GNP as determined by changes from baseline of interferon gamma and IL-10 ELISPOT responses to this peptide in draining axillary lymph node before treatment and following the last treatment administration.
- Changes in additional immunological biomarkers (e.g. flow cytometry profiles, T reg assays, autoantibodies, beta cell and T cell free DNA markers) from baseline at week 0, 9 and 14.

- Effects on residual insulin requirement and c-peptide secretion at week 14 as compared to baseline as assessed by a mixed meal tolerance test and a stimulated urine c-peptide test.
- Effects on glycaemic control assessed by blood sugar profiles and HbA1c at week 14 as compared to baseline
- Questionnaires on quality of life and diabetes self-management.

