#### **12.1.2 Immunological outcomes**

Change in level or quality of T lymphocyte biomarkers of  $\beta$ -cell specific immune response will be assessed at 14 weeks (8 weeks for lymph nodes sampling) versus baseline, Levels of T lymphocyte biomarkers are measured as the numbers of cytokine-producing T cells responding to PPI C19-A3 or other  $\beta$ -cell autoantigenic peptides and the numbers of cytokine and other immune gene transcripts produced in response to stimulation with PPI C19-A3 or other  $\beta$ -cell autoantigenic peptides in vitro. A potentially important biomarker of therapeutic efficacy would be an increase in the number of responder T cells synthesizing the immune regulatory cytokine IL-10, or a decrease in the number of responder T cells synthesizing the pro-inflammatory cytokines IFN- $\gamma$ .

Changes in the quality of the immune response can also be measured by assays that specifically detect the ability of post-treatment CD4 T cells to regulate pre-treatment pro-inflammatory responses.

Changes in the level or quality of islet cell autoantibody biomarkers of  $\beta$ -cell specific immune response will be measured at 0, 14 weeks and compared with levels at baseline and between

groups. A potentially important biomarker would be a reduction in levels of islet cell autoantibodies. Changes in serum levels of cell free DNA derived from beta cells and T cells will be measured to provide potentially important biomarkers of beta cell and T cell death.

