## **14 SAMPLE SIZE**

The single group study provides 8 patients on active treatment from whom it will be possible to collect safety data. This is considered optimal to achieve sufficient data to inform future study designs and on which to base future sample size calculations.

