5.1.2. Secondary outcomes

Differences in the parameters set below will be calculated for each patient and summarised by mean and standard deviations. Potential differences between patients receiving treatment within and outside treatment schedule will also be explored, if required.

- T cell responses to C19-A3 GNP as determined by changes from baseline of interferon gamma and IL-10 ELISPOT responses to this peptide in blood following treatment at weeks 0, 9 and 14.
- T cell responses to C19-A3 GNP as determined by changes from baseline of interferon gamma and IL-10 ELISPOT responses to this peptide in

draining axillary lymph node before treatment and following the last treatment administration (four aspirations: before and after visit 1 and visit 3)

- Changes in additional immunological biomarkers (e.g. flow cytometry profiles, T reg assays, autoantibodies, beta cell and T cell free DNA markers) from baseline at week 0, 9 and 14.
- Effects on residual insulin requirement and c-peptide secretion at week 14 as compared to baseline as assessed by secreted C peptide AUC after a mixed meal tolerance test and a stimulated urine c-peptide test.
- Effects on glycaemic control assessed by blood sugar profiles and HbA1c at week 14 as compared to baseline
- Scores on quality of life and diabetes self-management (week 0 and week 14).

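### Protocol 15.1 calls any baseline comparison with p<0.05 significant, with no multiplicity control, while the SAP plans descriptive statistics only; neither document says which governs

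*Protocol*

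**What the plan says.** Protocol 15.1 starts descriptively: "The analyses will mostly consist of tables of data such as mean values". It then adds hypothesis tests: "Comparisons against baseline will be made using Student's t-tests for paired and unpaired samples", together with the Mann-Whitney and Wilcoxon matched pairs tests, and the rule that "p values <0.05 will be considered significant". It assigns no test to any endpoint and ranks nothing. Protocol section 14 gives the size: "The single group study provides 8 patients on active treatment".

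The SAP reads differently. Section 4 says the sample was not powered for before/after differences and that simple descriptive statistics will be used. On the secondary outcomes, 5.1.2 says: "Differences in the parameters set below will be calculated for each patient and summarised by mean and standard deviations". The SAP contains no test and no p-value threshold.

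The time points for the blood T cell response also differ. Protocol 4.4 and SAP 5.1.2 look at "responses to this peptide in blood following treatment at weeks 0, 9 and 14". Protocol 12.1.2 says T lymphocyte biomarkers "will be assessed at 14 weeks (8 weeks for lymph nodes sampling) versus baseline". The same section names as a potentially important efficacy biomarker a rise in IL-10 producing cells "or a decrease in the number of responder T cells synthesizing the pro-inflammatory cytokines" (IFN-gamma), so either direction of evidence could be put forward.

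**The concern.** One unadjusted threshold applied to a long, unranked list of endpoints in 8 uncontrolled patients will often produce a nominally significant change by chance. Protocol 15.1 says the trial is meant to guide an immunotherapy programme and that data may be analysed early for that purpose. A chance result carrying the protocol's own label of significance could therefore be taken forward as evidence of an immune or metabolic effect, with no control group to check it against.

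The SAP's statement that the trial is not powered does not settle this. Low power concerns effects that are missed; it does not limit false positives. The SAP also does not withdraw the tests in 15.1.

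**Working it through.** **Figure to reproduce.** There is none. Neither document states a family-wise error rate, a power or a number of comparisons.

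**Inputs**
- n = 8 (Protocol 14).
- Threshold 0.05 per comparison (Protocol 15.1). Sidedness is not stated; two-sided is assumed.
- Paired t or Wilcoxon matched pairs test (Protocol 15.1), because each patient is compared with his or her own baseline.
- Correlation between endpoints: not given. An equal correlation of 0, 0.5 or 0.8 is assumed.

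**Step 1: count the comparisons** (Protocol 4.4, 10.3, 12.1 and 12.2)

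| Group | Week 14 only | Added by week 9 |
|---|---|---|
| Blood ELISPOT, IFN-gamma and IL-10 | 2 | 2 |
| Node ELISPOT, one contrast, two cytokines | 2 | – |
| Autoantibodies (insulin, GAD-65, IA-2, ZnT8) | 4 | 4 |
| Cell-free DNA (beta cell, T cell) | 2 | 2 |
| Flow cytometry, Treg assay (one readout each, assumed) | 2 | 2 |
| MMTT C-peptide, urine C-peptide, insulin use | 3 | – |
| HbA1c | 1 | – |
| CGM: MAGE, hypoglycaemia frequency, SD, IQR | 4 | – |
| HFS, ADDQoL, DTSQs | 3 | – |
| Total | 23 | 10 |

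With week 9 the total is 23 + 10 = 33. Leaving out the four CGM measures, which 4.4 does not name one by one, gives a strict count of 23 − 4 = 19.

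**Step 2: true level of one test.** For the paired t-test it is 0.05. For the exact Wilcoxon test with 8 pairs there are 2^8 = 256 sign patterns. A smaller rank sum of 3 or less occurs in 10 of them, 10/256 = 0.039. The next cut-off gives 14/256 = 0.055, which is too large. So the level is 0.039.

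**Step 3: chance of at least one false positive, independent endpoints:** 1 − (1 − a)^k.
- t: 1 − 0.95^19 = 0.62; 1 − 0.95^23 = 0.69; 1 − 0.95^33 = 0.82.
- Wilcoxon (a = 0.0391): 0.53, 0.60 and 0.73.

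**Step 4: correlated endpoints.** I simulated 100,000 null trials per setting, with 8 normal paired differences per endpoint and a common correlation.

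| Comparisons | t, 0.5 | Wilcoxon, 0.5 | t, 0.8 | Wilcoxon, 0.8 |
|---|---|---|---|---|
| 19 | 0.45 | 0.39 | 0.26 | 0.22 |
| 23 | 0.49 | 0.43 | 0.27 | 0.24 |
| 33 | 0.58 | 0.51 | 0.31 | 0.27 |

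The range is 0.39 to 0.58 at correlation 0.5. Over all settings it is 0.22 (19 Wilcoxon tests, correlation 0.8) to 0.82 (33 independent t-tests). The lowest value is 0.22/0.05 = 4.4 times the nominal level.

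**Step 5: expected number of false positives,** k × a, whatever the correlation. For t-tests it is 19 × 0.05 = 0.95 to 33 × 0.05 = 1.65.

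**Step 6: could alpha be split instead?** The smallest possible two-sided Wilcoxon p with 8 pairs is 2/256 = 0.0078. Bonferroni over 19 comparisons needs 0.05/19 = 0.0026. No rank test on 8 pairs could ever pass, so splitting alpha is not practical here.

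**Step 7: the SAP route.** With no tests, the number of p values is 0 and none of these error rates arises.

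**The case against.** The strongest reply is that the SAP already deals with this. SAP 2.3 requires a finalised, signed SAP before the final analysis starts, and that SAP plans only descriptive summaries. Protocol section 12 says the study was not primarily designed to assess efficacy and speaks only of possible trends. Section 13 gives a safety aim, section 14 presents the 8 patients as informing later designs, and 12.1.2 calls its biomarkers only potentially important. All of this stands, and it is why the point is modest. It does not remove the conflict: the significance rule is still in the protocol, the SAP does not withdraw it, and no precedence is stated.

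A reader might infer that a false significant immune or metabolic effect is about as likely as not. The documents do not support that as a general statement. It needs the protocol rule to be the one followed, and it rests on a correlation near 0.5 that no document gives; at 0.8 the chance is about 0.22 to 0.31. Three of the counted comparisons are questionnaires, neither immune nor metabolic.

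A reader might also take 23 comparisons as a minimum. It is not: 15.1 says the analyses are mostly tables, assigns no test to any endpoint, and 19 is a defensible count. On the other side, the count leaves out other islet peptides, gene transcripts and the additional node aspirations, so 33 is not a ceiling either.

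The time-point difference is narrow. Protocol 4.4 fixes C-peptide, insulin requirement, blood sugar profiles and HbA1c at week 14, and SAP 5.1.2 fixes the questionnaires at weeks 0 and 14. Only the blood immune markers carry week 9.

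**Conclusion.** The point holds as a conflict between the documents, with a real but conditional consequence. Followed as written, Protocol 15.1 gives a chance of at least one false significant secondary result well above 0.05: about 0.39 to 0.58 at correlation 0.5, and about 0.22 to 0.82 across the settings examined. These figures assume n = 8, no true effect, two-sided tests, normal differences, a common correlation, and 19 to 33 comparisons by my count. If the SAP alone is followed, the inflation does not occur. The excess over 0.05 does not depend on the exact count, the choice between t and Wilcoxon, or the correlation within the range shown; its size does. The primary safety endpoint is untouched. This is a low-cost improvement that limits what the secondary results may be said to show, not a flaw in the trial's main purpose.

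**What to change.** In Protocol 15.1, replace the sentence "p values <0.05 will be considered significant" with:

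*Comparisons against baseline are exploratory and descriptive, consistent with SAP section 4; no result will be declared statistically significant. Any p value shown is nominal, two-sided and unadjusted, and all listed comparisons will be reported with their number.*

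Also reconcile the blood T cell time points, so that Protocol 4.4, Protocol 12.1.2 and SAP 5.1.2 agree on whether week 9 is compared with baseline alongside week 14. Naming one lead immune readout is optional. It would help the reader, but it controls no error once nothing is declared significant.

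The cost is a few sentences, with no new data and no more patients. The downside for the sponsor is that an isolated secondary result can no longer be called significant.

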## **16 QUALITY ASSURANCE, SITE MONITORING AND DIRECT ACCESS TO SOURCE DATA AND DOCUMENTS**

The Investigator(s) will permit trial-related monitoring, audits, REC review, and regulatory inspections (where appropriate) by providing direct access to source data and other documents (ie patients' case sheets, blood test reports, X-ray reports, histology reports etc). Monitoring of this trial to ensure compliance with Good Clinical Practice and scientific integrity will be conducted by STU for the Cardiff site and Forum Östergötland at Linköping who will have direct access to source data.

Source documents produced for this trial will be kept in the patient's hospital records and source data will be transcribed into trial-specific Case Report Forms (CRFs) at the end of each patient visit. These CRFs will be coded with the study number and will not include patients' names and addresses.

Selected anonymised data will also be stored in electronic format. Paper records will be kept in a locked cabinet in secure premises at all times when the record is not in use for a study visit. Access to the records will be restricted to researchers working on the study, Sponsor representatives and representatives of regulatory authorities required to audit the conduct of the research study.

Relevant data will be transferred (with double data entry/data checking) from the paper record in the trial office to an electronic database which will be stored and regularly backed up on a Cardiff University server. Identifiable data including the link between the patients'

names and the study number will be stored separately from other data. All files will be password protected. Electronic data containing personalised information will be saved on Cardiff University computers only in password protected files and backed up regularly to hard copy on secure remote Cardiff University servers. Participant data will be anonymised by the use of study numbers. A copy of the study number code identifying subjects will be kept in a secure cabinet at local study sites accessible to the investigators at all times. Analysis will be conducted by the study team. Analysis will only be conducted on anonymised data.

The Chief Investigator, [name] will act as custodian of the data, however for practical purposes this role will be delegated to STU. Personal data will be stored for a minimum of 15 years. Access will be controlled by [name] who will continue to act as custodian for all data held by the Sponsor and will permit trial related monitoring, audits, REC review, and regulatory inspections (where appropriate) by providing direct access to source data and all other documents (i.e. patients' case sheets, blood test reports, etc).

## **17 ETHICS AND REGULATORY APPROVALS**

The trial will be conducted in compliance with the principles of the Declaration of Helsinki (2013), the principles of GCP and in accordance with all applicable regulatory requirements including but not limited to the Research Governance Framework and the Medicines for Human Use (Clinical Trial) Regulations 2004, as amended in 2006 and any subsequent amendments.

This protocol and related documents will be submitted via the Integrated Research Application System for review by a Research Ethics Committee (REC), Regional Ethical Review Board (RERB) and to the Medicines and Healthcare products Regulatory Agency (MHRA) for Clinical Trial Authorisation and to the Medical Products Agency (MPA) for approval.

The Chief Investigator will submit annual progress and safety reports and a final report at conclusion of the trial to the REC and the MHRA within the timelines defined in the Regulations.

## **18 FINANCIAL AND INSURANCE ASPECTS**

Support for this trial has been granted by the European Commission FP7 programme.

Cardiff University has arranged clinical research insurance to cover the legal liability of the University for negligent harm. In addition the study doctors hold substantive or honorary NHS contracts, giving them the protection of the NHS clinical negligence arrangements. Swedish patients will be covered by Patientskadeförsäkringen.

## **19 PATIENT INVOLVEMENT**

Involving patients from the outset strengthens the application by showing that the research is patient-centred and that patient participation has been welcomed, encouraged and facilitated. Our patient representative(s) will be involved in:

- Trial management meetings;
- Trouble shooting to support recruitment and retention of participants;
- Reporting the final results to the trial participants;
- Preparing information for web site inclusion.

The study will be registered on the NIHR INVOLVE and HCRW Involving People (Cynnwys Pobl) databases once ethical approval is granted. These are national advisory groups that support greater public involvement in NHS, public health and social care research. INVOLVE provides a public information pack, newsletters and public networking to facilitate public involvement. Locally, Involving People provides excellent training and support for public involvement via local conferences, newsletters and public network.

Patient involvement, will also facilitate dissemination of the study findings to as wide an audience as possible and will help set the agenda for future research in this field. Training and support for our patient representatives will be flexible and tailored to their individual needs. It will include training on the study background, methods and outcomes and where indicated IT training will be provided. Patients will be reimbursed in line with HCRW's AcoRD guidance (Attributing the costs of Health and Social Care Research & Development).

## **20 PUBLICATION POLICY**

It is intended that the results of the study will be reported and disseminated at international conferences and in peer-reviewed scientific journals. Written feedback will also be provided to the study participants.

## **21 TRIAL MANAGEMENT**

### **21.1 Trial Steering Committee (TSC)**

1. For a small phase 1 trial such as this, it is not considered that a TSC is required.

### **21.2 Trial Management Group (TMG)**

The project will be run by a Trial Management Group comprising PI's, trial manager, clinical research fellow, statistician (CTU staff), chief investigator and patient representatives and Sponsor representation. The TMG will oversee the day to day trial management and will meet in person or by teleconference at a minimum 2 monthly for the duration of the study. The TMG will overview and provide guidance on all aspects of regulatory approval, set-up, recruitment, protocol deviations, adverse events, data management, data analysis and dissemination. The TMG will report at agreed intervals to the DSMB and to the study sponsor.

### 21.3 Data safety Monitoring Board (DSMB) members:

An independent Data Safety Monitoring Board (DSMB) will be convened for the duration of the trial comprising a consultant diabetes physician, a clinical immunologist and a consultant rheumatologist. The DSMB will meet (face-to-face or by teleconference) at agreed intervals throughout the trial and receive reports of all adverse events from the Chief Investigator and/or other members of the trial team, as well as assessing progress in recruitment. The chairman of the DSMB may also call additional meetings as necessary. The DSMB will have responsibility for suspending or terminating treatment of one or a group of subjects if subject safety is considered at risk.

[figure not shown]

1.1. Introduction

This is the plan for analysing the safety, feasibility and efficacy endpoints from a Phase 1a study of gold nanoparticles administered intradermally by microneedles to deliver immunotherapy with a proinsulin derived peptide in Type 1 diabetes.

At diagnosis of Type 1 diabetes, most people have sufficient residual beta cell function to achieve good glycaemic control. This level of beta cell function, even if it declines or is lost over the next few years, has been shown to improve glycaemic control, reduce hypoglycaemia, improve quality of life and reduce long-term complications.

Antigen specific immunotherapy (ASI) is the preferred approach to beta cell preservation since this avoids the risks of immunosuppression. Attempts at ASI to date although successful in preclinical models have had limited efficacy in humans. There is therefore an urgent need for the development of novel approaches to deliver effective ASI.

The skin is a very effective means of antigen delivery to the immune system due to the very high density and specialised nature of its antigen presenting cells (APCs). Yet the density of APCs reduces rapidly just below the epidermis. The study will target antigen presentation through the superficial layers of the skin via the use of ultrashort needles to improve efficiency of antigen delivery.

To enhance uptake of antigen by dendritic cells and reduce inflammation, very small gold nanoparticles will be coupled to a peptide of proinsulin C19-A3. This peptide is a naturally processed and presented T cell epitope of proinsulin that is frequently targeted in patients with type 1 diabetes who carry the susceptibility molecule, HLA-DRB1*0401. Gold is an inert metal which has an extensive safety record and safety can be further enhanced by the use of very small nanoparticles. Preclinical data show that gold nanoparticles (GNP) coupled peptide has the potential to induce a regulatory T cell response not only in skin at the site of administration but at distance sites including the pancreas draining lymph nodes.

1.2. Objectives

The primary objective of the study is to examine the risk of C19-A3 GNP administration in terms of general safety and induction of hypersensitivity.

Secondary objectives are:

- To study the feasibility of delivering C19-A3 GNP via microneedles to humans.
- To study the size and nature of immune responses to C19-A3 GNP generated in blood and the draining (axillary) lymph node.

2. Study Methods

